In the present study, we aim to compare the diagnostic yield of Robotic-nCLE-guided TBNA for lung cancer diagnosis to conventional Robotic-guided TBNA using the final diagnosis (histology or follow-up) as the standard reference. Furthermore, we will create an image atlas of the characteristics of nCLE-images in PPNs. Also, we aim to describe tumor types based on in-vivo characteristics. Improved characterization of distal lung lesions might lead to improved and quicker cancer diagnosis and patient care.

Background: nCLE imaging of PPNs under bronchoscopic guidance is feasible and safe.

Primary objective:

To compare the first-pass diagnostic yield of the sequential needle passes (ROSE) between the Robotic-nCLE-guided TBNA arm and the Robotic- guided TBNA arm in PPNs.

Primary endpoint:

Increase of the first-pass diagnostic yield by 20%, from 70% to 90%, between Robotic-nCLE-guided TBNA arm and the Robotic- guided TBNA arm in PPNs.

Secondary objectives:

1. To compare the per-patient diagnostic yield (cumulative pass diagnostic yield: cumulative number of passes until five cumulated passes) of Robotic-nCLE-guided TBNA arm to that of Robotic-guided TBNA arm in PPNs.
2. To compare the proportion of patients with lung cancer treatment in the Robotic-nCLE-guided TBNA arm to that of the Robotic-guided TBNA arm in PPNs.
3. To compare the proportion of patients with follow-up (video-assisted thoracoscopic surgery (VATS) or TTNA or TBNA procedures) in the Robotic-nCLE-guided TBNA arm to that of the Robotic-guided TBNA arm in PPNs.
4. To compare the number of passes needed to obtain a final diagnosis of Robotic-nCLE-guided TBNA to that of Robotic-guided TBNA in PPNs.
5. To assess the diagnostic performance (sensitivity, specificity, PPV, NPV, accuracy) of the sequential cumulative nCLE passes and the sequential cumulative ROSE passes using the final diagnosis as a reference.
6. Feasibility: obtain adequate CLE video footage in >80% of the PPN punctures.
7. To assess the safety of nCLE imaging, as defined by:
 - a. The number and frequency of all AE/SAE from the start of the procedure until end of 12-month follow-up;
 - b. The number and frequency of nCLE procedure-related AE/SAE from the start of the procedure until end of 12-month follow-up.
8. To assess the reproducibility of nCLE criteria with regard to the reference standard. Three nCLE characteristics for the detection of malignancy were identified during Wijmans et al. study [10]:

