3. Lidocaine 10ml will be orally administered to provide local throat and tracheal anesthesia.
4. The bronchoscope will be introduced into the trachea.
5. After target localization (lung tumor), a guiding needle (FlexNeedle 18G, Broncus Medical) will be introduced in the working channel of the scope and on the placement of the endoscope within the bronchus in proximity to the target, the needle is introduced through the bronchial wall and into the lung tumor using fluoroscopy and r-EBUS guidance.
6. **(research-purposes) nCLE acquisitions will be obtained (only in patients in the ROBOTIC-nCLE-guided TBNA arm) by fitting the optical fiber into the TBNA needle and introducing it in the target lesions under fluoroscopy control.**
7. After the nCLE data is acquired and the probe is retrieved, cytological samples will be conducted following a standard protocol (ROSE).
8. Steps 6 and 7 will be performed for each pass.
9. The bronchoscope will be retrieved.

On completion of each procedure, the patients will be extubated and transferred to the recovery area. All patients will be monitored until discharge per standard institutional clinical protocol. This includes a chest x-ray post-procedure to determine whether the patient has suffered a pneumothorax. In the case of a pneumothorax, the complication will be treated with the institutional standard of care. The risks associated with the procedure are no different from a routine bronchoscopy and biopsy. There is a small increased risk

that a patient may have an allergic reaction to fluorescein. Again, this complication will be treated with the institutional standard of care.

nCLE analysis

Each nCLE-video will be analyzed in a blinded fashion to evaluate nCLE lung nodule and lymph node characteristics. The results of the nCLE video reviews will be compared to the corresponding cytological or histopathological results.

Three blinded raters will review nCLE videos for image quality, lung lesion detection and CLE characteristics.

Training session for CLE raters

nCLE raters with various backgrounds will be trained in the nCLE lung cancer criteria using powerpoint slides, hand-drawn schematics and a preselected set of training videos that had not been used previously. Training slides with hand-drawn nCLE lung cancer criteria schematics will also be provided.

Intra-procedure Interpretation of nCLE

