During the nCLE procedure the bronchoscopist will judge quality of the image, lung lesion detection, and presence of malignancy. The bronchoscopist will be trained in nCLE image evaluation.

Validation session

The trained raters will evaluate nCLE videos of all 59 patients as a randomized data-set and be blinded to the patient history and cytologic/pathologic diagnosis. Videos used for the training session will be excluded. The results of the nCLE video reviews will be compared to the corresponding cytological or histopathological results. The first session will be performed to assess the nCLE characteristics, image quality and confidence and will be used to calculate the inter-observer agreement (IOA) between the raters for detecting malignancies based on nCLE videos. The second session will be performed by the same group of raters, after a 2-week wash-out period, using the same set nCLE videos in a different order to assess the intra-observer reliability (IOR).

Pathological examination

During bronchoscopy, the sites suspected of malignancy will be evaluated with nCLE. In the case of positive tumor cytology (nodes/tumor) or histology (tumor), this will be the reference standard for the nCLE images. In the case of tumor negative cytology or histology, additional surgical/pathological staging or clinical/radiological follow-up will be available.

Cytological aspiration (standard procedure)

During the bronchoscopic procedure, the cytological aspirations will be evaluated on-site by a cytopathologist (ROSE). The appearance of cancer cells will be reported and shown on screen to the endoscopist. Definitive diagnosis of the sample follows after re-evaluation by a staff member of the pathological department. No additional samples will be taken for the research protocol, nor will the research protocol interfere with the pathological diagnostic protocol.

Histological evaluation

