- PPV: Probability that malignancy is present when sequential cumulative ROSE passes is positive: $= a/(a + b)$
- NPV: Probability that malignancy is not present when sequential cumulative ROSE passes is negative: $= d/(c + d)$

The same calculations will be performed for the different sequential cumulative nCLE passes. Diagnostic performances for both techniques will be compared using the DeLong and DeLong statistical method [26] with the final diagnosis as the reference diagnosis.

Per patient diagnostic yield (cumulative pass diagnostic yield) and performance calculations

Per patient diagnostic yield of each bronchoscopic procedure (Robotic-guided TBNA and Robotic-nCLE-guided TBNA) is defined as the proportion of patients whose procedure will yield a definitive diagnosis out of the total number of patients that have received that procedure. Two diagnostic yields will be calculated: one for the Robotic-guided TBNA arm and one for the Robotic-nCLE-guided TBNA arm. 95% confidence intervals will be calculated, and the p-value to compare diagnostic yield values between arms.

The diagnostic accuracies of a bronchoscopic procedure (Robotic-guided TBNA and Robotic-nCLE-guided TBNA) will be measured at the end of a follow-up period according to their sensitivities and specificities. The sensitivity test will measure the ability of a technique to correctly identify those patients with the disease (true positive rate). In contrast, the specificity test will measure the ability of the technique to correctly identify those patients without the disease (true negative rate). Sensitivity, specificity, positive predictive value (PPV), and negative predictive value (NPV) will be calculated as the accuracy of the Robotic-guided TBNA and that of Robotic-nCLE-guided TBNA diagnosis (based on final pathology results) compared to the definitive diagnosis based on all available procedures and follow-up.

Where a = true positive, b = false positive, c = false negative, and d = true negative:

- Sensitivity: Probability that a Robotic-guided biopsy will be positive when malignancy is present (true positive rate): $= a/(a + c)$
- Specificity: Probability that a Robotic-guided biopsy will be negative when malignancy is not present (true negative rate): $= d/(b + d)$
- PPV: Probability that malignancy is present when a Robotic-guided biopsy is positive: $= a/(a + b)$
- NPV: Probability that malignancy is not present when a Robotic-guided biopsy is negative: $= d/(c + d)$

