- Accuracy: Probability that a Robotic-guided biopsy gives correct prediction among the total number of cases examined: $= (a + d)/(a + b + c + d)$

Patient diagnostic and management analysis:

Intermediate and final diagnosis and management recommendation proportion differences for the two patient populations (Robotic-guided TBNA arm and Robotic-nCLE-guided TBNA arm) will be compared using a chi-square test. Intermediate and final diagnosis and management recommendation proportions will also be compared for the two patient populations. Differences between Robotic-guided TBNA and Robotic-nCLE-guided TBNA arms regarding the specific diagnostic and management categories will be compared using McNemar's test both at the intermediate diagnosis and the final diagnosis stage.

Feasibility statistical analysis:

The feasibility of needle-based lung cancer diagnosis will be assessed by investigating the following items:

- Assessing nCLE-image quality
- Assessing the feasibility of the integrated needle/Cellvizio® I.V.E Confocal Miniprobe™.

The imaging feasibility yield for the Robotic-nCLE-guided TBNA procedure is defined as the proportion of patients in whom procedure will yield at least good nCLE image quality out of the total number of patients that will receive that procedure.

The mechanical feasibility yield for the Robotic-nCLE-guided TBNA procedure is defined as the proportion of patients for whom Robotic-nCLE-guided TBNA procedure will be possible mechanically (meaning that the nCLE probe will be guided to the nodule successfully) out of the total number of patients that will receive that procedure.

Safety:

The safety will be assessed by carefully monitoring adverse events related to both procedures. Serious adverse event rates will be calculated by dividing the number of events for each procedure divided by the total number of procedures for each arm.

Reproducibility:

To assess the reproducibility of bronchoscopy guided nCLE:

- Estimating the reproducibility of nCLE criteria will be evaluated by calculating the inter-observer agreement of nCLE criteria between 3 readers (Fleiss Kappa).

In Wijmans et al. [10], three nCLE characteristics for the detection of malignancy were identified in different subtypes of lung tumors and metastatic lymph nodes:

- 1) dark enlarged pleomorphic cells;
- 2) dark cell clusters consisting of overlapping cell structures ('dark clumps'); and

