- 3) the continuous movement of a part of the cells in one direction ('directional streaming')

These criteria will be evaluated qualitatively.

New nCLE characteristics in malignant and benign lung lesions could also be identified during this study. An imaging atlas of nCLE images will also be built for the different tumor types on in-vivo characteristics. The department of pathology will be strongly involved in this project.

nCLE-video images will be reviewed and diagnosed retrospectively, independently, and blindly by investigators, expert readers, and pathologists.

The diagnostic yield will be tested to give the likelihood that nCLE will provide the information needed to establish a diagnosis.

Correlation analysis will also be performed between:

- nCLE imaging results and digital images of cytological or histopathological results
- nCLE imaging results in different tumor types.

8. End Points

Primary endpoint: The definitive diagnosis will serve as the reference standard for the calculation of study endpoints. The study pathologists will not be aware of nCLE results. The primary endpoint of this study will be the first-pass diagnostic yield, as defined in the section "Sample size calculation", i.e. and is calculated as the proportion of patients for which first-pass TBNA during the bronchoscopic procedure yielded a definitive diagnosis out of the total number of patients that have received a diagnostic procedure

Secondary endpoint: The secondary outcome of this study will be the per-patient diagnostic yield, calculated as the proportion of patients in whom the bronchoscopic procedure yielded a definitive diagnosis out of the total number of patients that have received a diagnostic procedure.

Third endpoint: The third endpoint for patient management will be assessing the clinical impact of nCLE by determining the proportion of patients with a correct change in definitive diagnosis and the associated change in management plan with nCLE.

First-pass diagnostic yield:

The study is designed to enroll 118 patients who will be randomly assigned 1:1 to Robotic-guided TBNA alone or Robotic-nCLE-guided TBNA for a statistical power of 80% with a 2-sided significance level of 0.05 to detect an increase of the primary study endpoint (per pass TBNA diagnostic yield) of at least 20%, from 70% to 90%, between the Robotic-guided TBNA and the Robotic-nCLE-guided TBNA.

Per patient diagnostic yield (cumulative pass diagnostic yield) and performance:

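### Objective 8 ties the three nCLE criteria to the reference standard, but the only statistic named for it is reader agreement and no per-criterion estimate against that standard is specified

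*Combined protocol and SAP*

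**What the plan says.** Objective 8, in the Section 1 Summary and again in the list of objectives before Section 3, is "To assess the reproducibility of nCLE criteria with regard to the reference standard". It names three features: enlarged pleomorphic cells, dark clumps and directional streaming.

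For this objective, Section 7 (Reproducibility) gives: "Estimating the reproducibility of nCLE criteria will be evaluated by calculating the inter-observer agreement of nCLE criteria between 3 readers (Fleiss Kappa". After listing the three features it adds: "These criteria will be evaluated qualitatively".

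Other parts of the plan bear on the same question:

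- Section 3 correlates each pass's cytopathology result with the nCLE sequence from that pass.
- Section 5 (nCLE analysis, and again Validation session) states: "The results of the nCLE video reviews will be compared to the corresponding cytological or histopathological results". Histological evaluation adds a comparison of digital slides with nCLE frames.
- Section 5 (Validation session) has a first reading session that scores characteristics, image quality and confidence and also yields "inter-observer agreement (IOA) between the raters for detecting malignancies based on nCLE videos". A second session after two weeks is for intra-observer reliability.
- Section 7 (Reproducibility) lists a correlation analysis of "nCLE imaging results and digital images of cytological or histopathological results".
- Section 7 (First- and cumulative-pass diagnostic yields), for objective 5, sets out sensitivity, specificity, PPV and NPV for ROSE against the final diagnosis and continues: "The same calculations will be performed for the different sequential cumulative nCLE passes".

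**The concern.** Kappa measures whether readers see the same thing. It does not measure whether what they see marks cancer. An objective that links the criteria to a reference standard needs a quantity that uses that standard, criterion by criterion. As written, an analyst could follow Section 7 fully and report objective 8 without any such quantity.

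The stake is limited but concrete. Objective 9 builds an atlas of malignant characteristics, and later users will take each of the three features as a marker of malignancy. If one of them is reproducible but uninformative in peripheral nodules, the planned outputs need not show it. Leaving the statistic, the reference and the unit open also allows them to be chosen after the data are seen.

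**Working it through.** **1. Figures in the plan.** The documents give no sample size, kappa target or precision for objective 8, so there is no figure of that kind to reproduce. The number of patients whose videos are read follows from the primary endpoint (Section 4, Sample size calculation). With the unpooled two-proportion formula, (1.960 + 0.842)² × (0.7×0.3 + 0.9×0.1) / 0.2² = 58.87, which rounds up to the stated 59 per arm. At the stated prevalence of 0.5, 59 × 0.5 = 29.5, which agrees with the plan's figure of at least 29 malignant nodules per arm. Neither figure is in dispute here.

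**2. What each planned analysis delivers for a single criterion.**

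- *Fleiss kappa (Section 7, Reproducibility):* agreement on the criteria. The reference standard does not enter.
- *Comparison of video reviews with cytology or histopathology (Section 5):* uses pathology, but names no statistic, and no analysis per criterion is stated.
- *Correlation analysis (Section 3; Section 7, Reproducibility):* uses pathology, but names no coefficient and is not stated per criterion.
- *Objective 5 accuracy (Section 7):* named statistics against the final diagnosis, but for the overall nCLE result. The plan does not say whether that is the on-site call or the blinded read. On site, the bronchoscopist judges quality, lesion detection and malignancy; scoring of the three features is not mentioned.
- *Second reading session (Section 5, Validation session):* Section 7 names no intra-observer statistic.

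No entry gives a per-criterion sensitivity, specificity or association measure. The reference also varies: corresponding cytology or histology in the Section 5 reading paragraphs, and the 12-month final diagnosis under Final Diagnosis and in Section 7.

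**3. Why kappa cannot stand in for it.** Assumed inputs, not from the documents: a feature present in 50% of nodules, with each reader wrong 10% of the time, independently.

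- Observed agreement between two readers = 0.9² + 0.1² = 0.82. Chance agreement = 0.50.
- Kappa = (0.82 − 0.50) / (1 − 0.50) = 0.64, and the same for three exchangeable readers.
- If the feature coincides with malignancy, each reader's sensitivity and specificity are both 90%.
- If it is independent of malignancy, a reader scores it present with probability 0.5×0.9 + 0.5×0.1 = 0.50 in either group, so both are 50%.

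Kappa is 0.64 in both cases. A simulation at the trial's size (59 videos, three readers, 9% error, feature independent of malignancy) gave a mean Fleiss kappa of 0.67, with central 95% range 0.52 to 0.82. Majority-read sensitivity and specificity averaged about 0.50.

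**4. What the planned reads could support.** With 29 malignant nodules, one read each:

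- 23/29 = 79%: Wilson 95% CI 62% to 90% (exact 60% to 92%).
- 15/29 = 52%: Wilson 34% to 69%. This overlaps the interval above.
- 26/29 = 90%: exact 73% to 98%. 14/29 = 48%: exact 29% to 67%. These do not overlap.
- Specificity on 30 non-malignant nodules is about as imprecise: 27/30 = 90%, exact 73% to 98%.

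The data could separate a strong criterion from an uninformative one, but not a moderate one.

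**The case against.** A reader might infer that the plan offers nothing beyond reader agreement and a qualitative look. The documents do not support that. Pathology comparisons or correlations appear in Sections 3, 5 and 7, and objective 5 gives nCLE accuracy against the final diagnosis. What stands is narrower: those comparisons name no statistic, and objective 5 does not address the criteria one at a time.

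A reader might also infer that invalid criteria could pass objective 8. It has no pass threshold, and Section 8 does not list reproducibility as an endpoint. If the malignancy call rested wholly on uninformative features, objective 5 would probably show poor accuracy. The real exposure is one weak criterion among three.

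The 90% accuracy and kappas of 0.68 and 0.70 in Section 1 could be taken for targets. They are an earlier study's results, given as background.

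The statement on qualitative evaluation may only mean that features are scored present or absent, which would suit a Fleiss kappa. That is possible, but it would still leave no estimate against the reference. Agreement on the malignancy call in Section 5 and on the criteria in Section 7 can likewise be read as complementary.

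Finally, one might claim that nodules with many passes would dominate the kappa. The plan never says kappa is per video, and dominance is not shown. If 53 of 59 patients had one pass and 6 had five (an assumption based on the 90% yield target), those 6 would give 30 of 53 + 30 = 83 videos, or 36%. The unit and the handling of repeated videos do still need stating.

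**Conclusion.** The concern holds in a limited form. Objective 8 refers to a reference standard that its only named statistic does not use, and no other planned analysis states a per-criterion estimate. A single reproducible but uninformative criterion could go unnoticed.

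This follows from setting the sections side by side and needs no assumed figure. The kappa of 0.64 with either 90% or 50% accuracy rests on assumed prevalence and reader error. It shows the principle and does not size an effect in this trial. The intervals assume 29 malignant nodules and one read per nodule.

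The matter concerns a descriptive secondary objective and the atlas. The primary comparison of first-pass yield is untouched. It is worth correcting because the reads are already planned.

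**What to change.** In Section 7, Reproducibility, replace the sentence on qualitative evaluation with a specified analysis:

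- For each of the three criteria and for the overall malignancy call, report sensitivity and specificity with 95% CIs from the blinded first-session reads, stating how the three readers' scores are combined.
- Name one reference, the final diagnosis. Add a sensitivity analysis against the corresponding per-pass cytology or histology, so that a needle outside the nodule is not counted as failure of the criterion. For the same reason, do not restrict the analysis to first-pass videos.
- Report inter-observer kappa (session 1) and intra-observer kappa (session 1 against session 2) for the same items.
- State the unit of analysis and use intervals that allow for several videos per patient, such as a patient-level bootstrap.
- Describe the results as estimation, without a formal test.

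The cost is SAP wording and a little more analysis. No extra reader, reading session or procedure is needed. The drawback is wide intervals with about 29 malignant nodules, which the report should show plainly.

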The biopsy results can be classified into three categories: positive results, including malignant or benign lesions confirmed by a follow-up period, or negative results, including [18] intermediate histological samples, such as chronic inflammation, organizing pneumonia, or atypical cells without sufficient features to ascertain malignancy; or [22] indeterminate samples, such as normal lung tissue or insufficient sample size [6]. The tissue samples that produce intermediate and indeterminate samples should be further evaluated according to recommended guidelines for the management of pulmonary nodules.

In this study, the diagnostic yield of the bronchoscopic procedure (Robotic-guided TBNA or Robotic-nCLE-guided TBNA) will be defined as the proportion of patients in whom the bronchoscopic procedure yield a definitive diagnosis out of the total number of patients that have received the diagnostic procedure. This value is affected by the lesions' sizes, locations, and the existence of a bronchus sign or an airway leading directly into the lesion [23].

Primary objective:

To compare the first-pass diagnostic yield of the sequential needle passes (ROSE) between the Robotic-nCLE-guided TBNA arm and the Robotic-guided arm in PPNs.

Secondary objectives:

[figure not shown]
1. To compare the per-patient diagnostic yield (cumulative pass diagnostic yield: cumulative number of passes until five cumulated passes) of Robotic-nCLE-guided TBNA to that of Robotic-guided TBNA in PPNs.
2. To compare the proportion of patients with lung cancer treatment in the Robotic-nCLE-guided TBNA arm to that of the Robotic-guided TBNA arm in PPNs.
3. To compare the proportion of patients with follow-up (video-assisted thoracoscopic surgery (VATS) or TTNA or TBNA procedures in the Robotic-nCLE-guided TBNA arm to that of the Robotic-guided TBNA arm in PPNs.
4. To compare the number of passes needed to obtain a final diagnosis of Robotic-nCLE-guided TBNA to that of Robotic-guided TBNA in PPNs.
5. To assess the diagnostic performance (sensitivity, specificity, PPV, NPV, accuracy) of the sequential cumulative nCLE passes and the sequential cumulative ROSE passes using the final diagnosis as a reference.
6. To assess the feasibility by obtaining adequate CLE video footage in >80% of the PPN punctures.
7. To assess the safety of nCLE imaging, as defined by:

- a. The number and frequency of all AE/SAE from the start of the procedure until end of 12-month follow-up
- b. The number and frequency of nCLE procedure-related AE/SAE from the start of the procedure until end of 12-month follow-up
- 8. To assess the reproducibility of nCLE criteria to the reference standard. Three nCLE characteristics for the detection of malignancy were identified during Wijmans et al. study [10]:
 - a. Dark enlarged pleomorphic cells;
 - b. Dark cell clusters consist of overlapping cell structures ('dark clumps') and
 - c. Continuous movement of the cells in one direction ('directional streaming').
- 9. To create an nCLE image atlas for malignant characteristics in PPNs.

3. Study Design

This is a randomized, controlled, interventional, comparative prospective multi-center study. In total, a maximum of 118 consecutive patients with a (suspected) PPN who are referred for a diagnostic bronchoscopic (Robotic-guided TBNA) procedure will be considered for enrollment. The estimated duration of the study is 24 months. Patients will be consecutively recruited and randomly assigned to undergo Robotic-guided TBNA (n=59) or Robotic-nCLE-guided TBNA (n=59).

Only patients in the nCLE arm will receive intravenously administered fluorescein before the start of the Robotic procedure. During the nCLE procedure, an 18G needle enters the targeted tissue, followed by an nCLE AQ-Flex™ 19N Confocal Miniprobe™ (Mauna Kea Technologies, France) through the biopsy needle, to obtain real-time imaging. nCLE imaging will be performed in the PPNs with a total estimated time for research measurements of 10 minutes. nCLE imaging will be performed for each sequential TBNA pass/sampling within the lung nodule lesion and each TBNA path cytopathological result will be correlated with the nCLE sequence acquired for that TBNA pass. TBNA sampling will end when sufficient diagnostic material will be found with ROSE (as assessed by the cytopathologist) or when the physician performing the procedure judges that the number of samplings/passes is adequate. ROSE will be performed by a cytopathologist.

4. Study Population

Population (base)

Patients with a PPN referred for diagnostic bronchoscopic/endosonographic workup tissue sampling based on standard (PET-) CT imaging

Inclusion criteria

To be eligible to participate in this study, a study subject must meet all of the following criteria:

- ≥ 21 years of age
- Suspected PPN
- Nodule size in CT between 8 mm and 30 mm (largest dimension)
- Ability to understand and willingness to sign a written informed consent and HIPAA consent document

Exclusion criteria

- Inability or non-willingness to provide informed consent
- Failure to comply with the study protocol
- Patients with known allergy for fluorescein or risk factors for an allergic reaction
- Use of beta-blocker within 24 hours before the start of the bronchoscopic procedure
- Possibly pregnant, pregnant or breastfeeding women
- Patients with hemodynamic instability
- Patients with refractory hypoxemia
- Patients with a therapeutic anticoagulant that cannot be held for an appropriate interval before the procedure
- Patients who are unable to tolerate general anesthesia according to the anesthesiologist
- Patient undergoing chemotherapy

Intra-operative Exclusion/Stopping Criteria:

- The lesions are unable to be localized/confirmed by bronchoscopy
- The procedure will be terminated if the patient develops a significant procedural complication as determined by the treating physician
- The procedure will be terminated if the patient develops hemodynamic instability as determined by the treating physician

Sample size calculation

A bronchoscopic TBNA (Robotic-guided TBNA or Robotic-nCLE-guided TBNA) will be regarded as successful when histological confirmation of the diagnosis is achieved and matches the final diagnosis. If additional TBNA passes or tests, e.g., further bronchoscopies, surgery, etc., are needed to establish the diagnosis, the TBNA pass will be regarded as non-diagnostic.

We will calculate TBNA diagnostic yield for the cumulative number of passes until five cumulated passes for both the Robotic-guided TBNA and Robotic-nCLE-guided TBNA arms. It is anticipated that sequential passes at a target site will result in stepwise yield increments to a plateau. Every needle pass at a location will be reported separately and entered into a database to provide yields after each sequential pass.

Proportional data will be compared using a Chi-squared test of contingency tables or Fisher's exact test on 2x2 contingency tables in the case of very small counts (<5).

First- and cumulative-pass diagnostic yields:

Diagnostic yields for the different cumulative passes are defined as follows:

1. First-pass diagnostic yield is calculated as the proportion of patients for which first-pass TBNA during the bronchoscopic procedure yielded a definitive diagnosis out of the total number of patients that have received a diagnostic procedure.
2. First-two-passes cumulative diagnostic yield is calculated as the proportion of patients for which first-two-passes cumulative TBNA pass during the bronchoscopic procedure yielded a definitive diagnosis out of the total number of patients that have received a diagnostic procedure.
3. First-three-passes cumulative diagnostic yield is calculated as the proportion of patients for which first-three-passes cumulative TBNA pass during the bronchoscopic procedure yielded a definitive diagnosis out of the total number of patients that have received a diagnostic procedure.
4. Etc.... until the fifth pass.

The number of patients has been calculated to demonstrate an increase of the TBNA first-pass diagnostic yield by 20%, from 70% to 90%, between the Robotic-guided TBNA and the Robotic-nCLE-guided TBNA, with a statistical power of 80% with a 2-sided significance level of 0.05. A group size of 59 patients per arm has been derived. By including 59 patients in each arm, we expect to image at least 29 malignant nodules (prevalence of 0.5) in each arm.

The study will enroll 118 consecutive patients randomly assigned 1:1 to Robotic-guided TBNA arm or Robotic-nCLE-guided TBNA arm.

5. Treatment of Subjects

Investigational product/treatment

In recent years, confocal laser endomicroscopy (CLE) has emerged as a novel technique that enables *in vivo* microscopic analysis during ongoing endoscopy [24]. CLE is based on tissue illumination with a low-power laser with subsequent detection of the fluorescence light reflected from the tissue. It is a contrast-based technique, the most widely used agent being the intravenously administered fluorescein. The probe of the endomicroscopy system consists of a flexible catheter probe representing a bundle of optical fibers linked to a micro-objective, a laser scanning unit, and the control and acquisition software (Cellvizio® I.V.E system, Mauna Kea Technologies, France). The principle of the technique is based on a laser beam of the defined wavelength being focused towards the targeted tissue, and the recaptured signal is displayed as 'optical biopsies' in a single horizontal plane.

[figure not shown]

Figure 1: A- Locking of the CLE probe to the aspiration needle. B- CLE probe inside endosonography needle. C- Endosonography images of n-CLE measurements (white arrow) inside a lymph node (LN) (Wijmans/Annema et al. [10]).

The advantage of nCLE is that it can provide real-time information on a microscopic level of tissues within a solid organ. Therefore, immediate validation of a biopsy location and outcome is possible. Since a needle is used to deliver the optical imaging probes, cell seeding is probably minimal since no tissue is removed by force or taken out of position. For the nCLE procedure, the Confocal Miniprobe™ (AQ-Flex™ 19 N Confocal Miniprobe™, Mauna Kea Technologies, France, was cleared by the FDA for TBNA procedures (K183640)) has been recently designed. This probe is small enough to fit through an 18G aspiration needle, has a resolution of 3.5 μ m, and has a penetration depth of 40-70 μ m.

[figure not shown]

Figure 2: Image (Wijmans/Annema et al. [10]) of EUS guided nCLE in lung cancer patients. nCLE imaging on top with corresponding cytology (lymph node capsule, stroma, vet, vasculature – from left to right)

Summary of known and potential risks and benefits

Fluorescein is a standard used dye in hospitals, where it is used primarily as a contrast dye to visualize the ocular vascular network. In patients without a known allergy to fluorescein, beta-blocker use, or pregnancy, the use of fluorescein is safe. In an extensive prospective review of 11,898 patients undergoing an angiogram with intravenous administration of fluorescein, 132 adverse events were recorded (1.1%) with the most typical reactions being nausea and vomiting [13]. No severe adverse reactions or deaths occurred. Adverse reactions on intravenous administration are rare and primarily mild reactions (Table 1). Fluorescein is widely used in studies with CLE, where it has proved to be safe and easy to perform [10–12].

Table 1. Different types of adverse reactions

Classification	Types of adverse reaction	No. of adverse reactions (%)
Mild	Nausea	87 (0.7)
	Vomiting	47 (0.4)
	Dizziness	34 (0.3)
Moderate	Faint	17 (0.1)
	Localized reactions	14 (0.1)
	Urticaria	28 (0.2)
Severe	Seizure	0 (0.0)
	Myocardial infarction	0 (0.0)
	Anaphylactic attack	0 (0.0)
Death		0 (0.0)

Table 1 Type and number of adverse reactions after intravenous administration of fluorescein in patients undergoing fluorescein angiography (n=11,898). (Kwan et al. 2006)

In 2010, Wallace et al. [14] published a retrospective study of all CLE procedures performed between January 2003 and November 2008, or 2,272 procedures (performed under protocol only), and no serious adverse events related to fluorescein injection were identified.

Most recently, in January 2018, Cellvizio® was recommended by the Korean National Health Agency (NECA, New Health Technology Assessment Committee) and obtained the Innovative Technology status. This recommendation was based on a systematic review of the literature on CLE and allowed the NECA to recognize endomicroscopy as "a safe and effective method that can help identify cancerous lesions and target biopsies for patients with suspected dysplasia in the esophagus, stomach, and bile duct stenosis." In this evaluation ([nHTA Report](https://nhta.neca.re.kr/nhta/publication/u0601vfd.ecg?pub_seq=572&file_kind=E) / Submission No. HTA-2018-16 *Abstract (English)* : https://nhta.neca.re.kr/nhta/publication/u0601vfd.ecg?pub_seq=572&file_kind=E, *Full text* : https://nhta.neca.re.kr/nhta/publication/u0601vfd.ecg?pub_seq=572&file_kind=F), the NECA evaluated the safety of CLE by examining 17 articles to identify complications and side effects associated with endomicroscopy with fluorescein injection. From this review, the NECA subcommittee evaluating the safety of endomicroscopy noted:

- that the complications or side effects identified in this literature review showed no difference between an endoscopy procedure without endomicroscopy and an endoscopy with endomicroscopy and fluorescein injection, and,
- most studies have not reported any serious side effects or complications.

The NECA subcommittee, therefore, concluded that the safety of the technology is of an acceptable level. So far, all the studies that investigated nCLE use showed that no adverse events occurred. Most studies investigated nCLE combined with EUS, and only one case report examined the Robotic guided nCLE and reported no adverse events.

[figure not shown]
[figure not shown]
Study procedures

Preparation before the procedure

Before beginning the procedure, a locking device is attached to the proximal end of a standard TBNA puncture needle (Bronchus 18G needle). To do so, the metallic stylet originally in the needle must be removed.

1. Removal of the stylet from the needle	2. Locking of the locking device onto the proximal needle hub
 	 

